2.6 Preservation and Confidentiality of Information

The researcher preserves all research data, including confirmation of all participants (able to effectively verify different record materials, such as hospital original records), all original informed consent forms with subject signatures, all case observation forms, detailed records of evaluation indicators, etc.

The results of this project may be published in medical journals, but we will keep the information of the subjects confidential in accordance with legal requirements. Unless required by relevant laws, the personal information of the subjects will not be disclosed. When necessary, research supervision and management departments, hospital ethics committees and their relevant personnel may access patient information in accordance with regulations.

3. Exit and Termination Criteria

- 1) Those who do not receive regular exercise guidance from doctors, which affects the accuracy and effectiveness of research;
- 2) Those who experience adverse events and are not suitable for further observation;
The doctor determines that it is not suitable to continue observing the patient;

- 3) The subject experiences certain serious complications or complications, death or loss of follow-up, and is deemed unsuitable for further observation by the doctor;
- 4) During the research process, participants experienced endpoint events such as cardiovascular and cerebrovascular events and death.

4 Ethical issues

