2.2 Study Description

The aim of this study is to observe the therapeutic effect of Baduanjin on improving shoulder joints in MHD patients. A total of 60 maintenance hemodialysis patients will be included and randomized into an intervention group of 30 cases and a control group of 30 cases. The intervention group underwent a 30 minute Baduanjin exercise under the guidance of a professional doctor before the dialysis day, including a 5-minute warm-up exercise, a 20 minute Baduanjin exercise, and a 5-minute relaxation exercise. The intervention group practice Baduanjin three days a week, while the control group maintain routine treatment and daily activities. Measure the indicators of each group at baseline, months 6, 12, and 18. The evaluation of shoulder joint function is based on the shoulder Constant score (which includes three dimensions: pain, daily living activities, and active range of motion); The quality of life score is based on the SF-12 score, and the emotional score is based on the Anxiety and Depression Scale.

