2.4 Outcome Measures

Primary Outcome Measure:

1) Shoulder joint function score

Using the adjusted version of the CMS scoring scale, the total score is 75 points, including pain (15 points), daily living ability (ADL, 20 points), and joint range of motion (ROM, 40 points).

2) Shoulder joint internal rotation function

The patient takes a standing position and measures the distance between the fingers and vertebrae of the hemodialysis patient's fistulae and non fistulae hands, that is, the patient moves their thumb with the backhand as much as possible along the midline of the back, and uses a tape measure to measure the closest distance from the tip of their thumb to the spinous process of the 7th cervical vertebra. Relevant data is organized and recorded.

3) Muscle strength measurement

Grip strength can reflect the strength of the hand muscles, and a grip strength meter is used to measure the grip strength of the patient's hands separately. The patient takes a standing position, holds the handle with maximum force, and records the value when the number on the machine display screen no longer changes. Test three times, take the maximum value, and record the relevant results.

4) Area of biceps brachii muscle

Measure the thickness of the biceps brachii muscle in two groups of patients through skeletal muscle ultrasound examination.

Secondary Outcome Measures:

1) Changes in the Short Form-36 (SF-36) and European Quality of Life Five Dimension (EQ-5D-5L)

Changes from the Short Form-36 (SF-36) and European Quality of Life Five Dimension (EQ-5D-5L) scale at 0 months, 8 months, 12 months. The SF-12 score is used to evaluate an individual's health status and quality of life. The SF-12 score expressed as a number between 0 and 100, with higher numbers indicating better health. EQ-5D-5L evaluate quality of life from five aspects: action ability, self-care, daily activities, pain or discomfort, anxiety or depression. The score range generally ranges from less than 0 to 1, and the higher the score, the better the state; The VAS score range is 0-100, with

higher scores indicating better health status.

2) Changes in the Hospital Anxiety and Depression Scale (HADS)

Changes from HADS Index at 0 months, 8 months, 12 months. HADS consists of 14 items, of which 7 items assess depression and 7 items assess anxiety. The scores for anxiety and depression range from 0 to 21, with higher scores indicating more severe symptoms.

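### Exit criterion 1 can remove randomised patients from the Baduanjin arm only, and the supplied text does not say whether exited patients are still assessed or analysed

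*Combined protocol and SAP*

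**What the plan says.** The first item in section 3 (Exit and Termination Criteria) is "Those who do not receive regular exercise guidance from doctors, which affects the accuracy and effectiveness of research". It names no arm, sets no threshold for regular guidance, and does not say what exit means for later visits.

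Section 2.2 describes who gets guidance. For the Baduanjin arm: "The intervention group underwent a 30 minute Baduanjin exercise under the guidance of a professional doctor before the dialysis day". The controls are described differently: "while the control group maintain routine treatment and daily activities". The 60 patients are randomised 30 to each arm, and the visit plan is "Measure the indicators of each group at baseline, months 6, 12, and 18", with no provision for those who have exited.

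The next two exit criteria tie exit to the end of observation: "Those who experience adverse events and are not suitable for further observation" and "and is deemed unsuitable for further observation by the doctor". Section 2.6 says "The researcher preserves all research data", which concerns archiving. Section 2.5 plans a t-test or a nonparametric test between two groups at P<0.05. In the supplied text it defines no analysis population and no handling of missing outcomes.

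**The concern.** Randomisation protects a comparison of everyone randomised. Criterion 1 acts after randomisation, depends on receipt of the assigned treatment, and has no counterpart in the control arm. If those who miss guidance are no longer measured or analysed, a Baduanjin arm reduced to its adherent members is compared with a complete control arm.

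The result favours Baduanjin if patients who miss guidance have worse shoulders. It favours control if they have better ones, and it is unbiased if receipt is unrelated to outcome. A relation is plausible: follow-up runs to month 18, and section 1 describes patients whose motor ability declines as the disease progresses. The reason given in criterion 1 concerns the quality of the research, not safety, so it points towards removing non-adherent patients from the results.

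**Working it through.** **Step 1: which arm the rule can act on.** Section 2.2 gives doctor guidance to the Baduanjin arm and routine care to controls. Read literally, criterion 1 would describe every control, which cannot be intended. It works only as a non-adherence rule in the Baduanjin arm. The other exit criteria (adverse events, complications, death, loss to follow-up, endpoint events) can apply to either arm.

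**Step 2: what happens after exit.** Nothing in sections 2.2, 2.4, 2.5, 2.6 or 3 as supplied answers this. The section heading and the observation wording of criteria 2 and 3 make the end of assessment the natural reading. That is an inference.

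**Step 3: illustration of size.** The plan gives no exit rate, SD, effect size or power, so there is no figure of its own to reproduce.

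- From the plan: 30 per arm, significance level 0.05 (two-sided assumed).
- Assumed: no true effect; one outcome with SD 1; the lowest 3, 6 or 9 of the 30 Baduanjin patients on a latent normal receipt score exit and are dropped; that score has correlation r with outcome.

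Bias = r × m, where m is the expected mean score of those who stay. From normal order statistics, m = 0.186, 0.338 and 0.483 for 3, 6 and 9 exits. For example, r = 0.5 with 9 exits gives 0.5 × 0.483 = 0.24 SD.

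The correlation of outcome with actual yes/no receipt is smaller: r × φ(q)/√(f(1−f)), where f is the exit share and q its normal quantile. The factor is 0.585, 0.700 and 0.759 for f = 10%, 20% and 30%.

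| r | Yes/no correlation (10/20/30% exit) | Bias, SD | Type I error, t-test |
|---|---|---|---|
| 0 | 0 | 0 | 5.0 / 5.1 / 5.1% |
| 0.3 | 0.18 / 0.21 / 0.23 | 0.06 / 0.10 / 0.14 | 5.7 / 6.7 / 8.0% |
| 0.5 | 0.29 / 0.35 / 0.38 | 0.09 / 0.17 / 0.24 | 6.7 / 9.7 / 14.1% |
| 0.7 | 0.41 / 0.49 / 0.53 | 0.13 / 0.24 / 0.34 | 8.4 / 15.2 / 23.9% |

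The error rates come from 200,000 simulated null trials per cell.

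Hand check of one cell (r = 0.5, 9 exits, so 21 against 30): the standard error is √(1/21 + 1/30) = 0.2845, and the bias in standard errors is 0.2415/0.2845 = 0.849. Type I error ≈ Φ(0.849 − 1.96) + Φ(−0.849 − 1.96) = 0.133 + 0.002, about 13.6%. The simulated 14.1% is consistent with this.

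**Step 4: variations.**

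- At r = −0.3 the error is 5.6/6.6/8.0%, mostly favouring control (false results favouring Baduanjin: 1.6/1.0/0.7%).
- The Mann-Whitney test gives nearly the same: 5.6/6.8/8.0% at r = 0.3, 6.8/9.6/13.4% at 0.5, and 8.1/14.3/22.6% at 0.7.
- Three random control exits barely change the t-test: 5.6/6.6/8.0%, 6.6/9.7/13.5% and 8.4/14.8/23.1%.

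**Step 5: power if everyone is kept.** Assume receivers gain 0.74 SD and non-receivers nothing. The average effect is 0.74 × 0.9 = 0.67, 0.74 × 0.8 = 0.59, or 0.74 × 0.7 = 0.52 SD. Simulated power with 30 against 30 falls from 80.5% to 70.8/59.9/48.2%. With non-receivers dropped (27, 24 or 21 against 30) it is 78.2/75.6/72.3%, but that comparison is unbiased only if receipt is unrelated to outcome.

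**The case against.** The strongest reply is that the harm depends on a procedure the plan never states. Criterion 1 lacks the observation wording of its neighbours, so exit could mean only that supervised exercise stops. The one-arm reading is also inferred, and the qualifier about accuracy and effectiveness may confine the rule to a few serious cases. On this view the defect is an undefined term and an unnamed analysis set, and a clarifying sentence would do.

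Part of this stands. Both readings are inferences, the number of exits could be small, and bias is a risk, not a stated procedure. But the text leaves study staff free to end follow-up in one arm for missed treatment, and nothing in the supplied analysis section would undo it. Keeping the criterion with an explicit statement that exit does not end assessment or analysis would have much the same effect as the fix below.

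The upper figures also need care. With 30% exits and r = 0.7, stayers and leavers differ by 0.483/0.3 × 0.7 = 1.13 SD, which is large. At r = 0.5 the gap is 0.81 SD. If change from baseline were analysed, the relevant correlation could differ. The rating therefore rests on the one-arm rule, not on these figures.

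Adverse-event exits could also fall unequally between an exercise arm and routine care. That is true, and it is a further reason to state a rule for missing outcomes.

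**Conclusion.** The concern holds and should be fixed. Followed on its natural reading, criterion 1 selects one arm after randomisation on receipt of its treatment, and the supplied text offers no safeguard. The statement of absence is limited to the supplied text, since some passages were removed before review.

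Direction and size cannot be known from the plan. Under the stated assumptions the consequence runs from none (receipt unrelated to outcome), through negligible (r = 0.3 with 10% exits, 5.7% type I error), to serious (14% at r = 0.5 with 30% exits; 24% in the extreme case). Confidence is medium, because what exit means is inferred.

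**What to change.** 1. Remove criterion 1 as a ground for leaving the study. Record missed guidance as non-adherence, with the reason (not attended or not delivered).
2. Keep these participants in every scheduled outcome assessment unless they withdraw consent.
3. Compare all randomised participants in their assigned arm. The section 2.5 tests can stay. State a rule for missing outcomes and one simple sensitivity analysis, for example shifting missing Baduanjin values by stated amounts. Because the direction of bias is unknown, shift them both ways.
4. Label any analysis restricted to those who received guidance as supplementary, and report exits by arm and reason.

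Criteria 2 to 4 are untouched, so some missing data will remain. Two related points need settling so that the rule can be written. The assessment months differ between section 2.2 (6, 12 and 18) and the secondary outcomes in section 2.4 ("Changes from HADS Index at 0 months, 8 months, 12 months"), and must be reconciled. Section 2.4 also lists four primary outcomes without a primary time point, so the rule should be stated for each.

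The direct cost is amendment wording and slightly more follow-up, in patients who already attend dialysis three times a week. The real cost is the dilution shown above: power of about 71%, 60% or 48% instead of 80% at 10%, 20% or 30% non-receipt, and lower still if non-receivers did worse than controls. This is the price of estimating the effect of being assigned to Baduanjin without selecting one arm.

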4.1 Ethical Approval

This clinical research protocol complies with the relevant provisions of the Helsinki Declaration regarding the protection of subject rights. This protocol, written informed consent form, and materials directly related to the subjects must be submitted to the ethics committee for written approval before the study can be officially conducted. If this protocol has been revised during the clinical research implementation process, it must be submitted to the ethics committee for approval before implementation, and these changes cannot be implemented without the approval of the ethics committee, unless they are made to eliminate obvious and direct risks to the subjects. When such situations occur, they will be reported to the ethics committee. If important new information related to the study is found, the informed consent form must be modified in writing and submitted to the ethics committee for approval before obtaining the consent of the subjects again. Each clinical research center agrees that before the start of this research project, the ethics committee of the team leader unit shall review the research plan. The ethics committees of each sub center may choose to file or review it themselves. If necessary (such as serious adverse events or protocol violations), the ethics committees of each center shall convene a meeting in a timely manner for review and report the review conclusions to the ethics committees of other centers.

